6.2.2 Secondary Objectives

The secondary objectives of the protocol are:

1. To assess PrEP coverage of sexual acts (prevention-effectiveness adherence) as measured by DOT Diary

We will estimate the probability of coverage of condomless receptive sexual acts in each period, with sexual acts treated as trials, and coverage as success. Confidence intervals will be obtained using GEE binomial models, with robust standard errors will be used to account for within-subject correlation as well as over-dispersion of the binomial outcome.

MSEs. We also used EPIC data to estimate the average number of condomless receptive sexual acts per participant as ~7. Under this assumption, we will be able to estimate coverage probabilities within MSEs of 4-10 percentage points, depending on coverage levels and the ICC of coverage across episodes.

2. To evaluate the daily use of the DOT and diary components of DOT Diary through 24 weeks of follow-up

We will estimate the average use of DOT and the diary, as proportions of days and weeks on study, respectively.

MSEs. Proportions will be estimated within MSEs of 7-12 percentage points, depending on the sample proportions.

6.2.3 Qualitative Data analysis

Recordings of the in-depth interviews (IDIs) will be analyzed using MAXQDA software for qualitative analysis. The analysis team will include members at both San Francisco and Atlanta study site, as well as a representative from AiCure. Interviewers will complete a debrief report promptly following each interview to capture results relevant to the study objectives. Debrief reports will also include an assessment of whether the interview merits additional in-depth analysis. Debriefing reports have been shown to be of sufficiently high quality to use as a primary source.³¹ Debrief reports and selected transcripts will be reviewed for emergent themes and results relevant to the study objectives. Team members will create summary reports based on this analysis for use in providing feedback and suggestions in achieving study goals, and to contribute to manuscript development. Debrief reports will be reviewed promptly in order to provide feedback and suggestions for subsequent interviews. The first two audio recorded interviews and resulting debrief report at each site will be reviewed by a member of the team at the other site in order to assure uniformity in interview approaches and information included in debrief reports.

7.0 Safety Monitoring and Adverse Event Reporting

7.1 Safety Monitoring and Clinical Data Review

A multi-tiered safety review process will be followed for the duration of this study. Close cooperation between the Protocol Chair, study site investigators, study coordinator, statistician, and other study team members will be necessary to monitor participant safety and to respond to occurrences of toxicity in a timely manner. The research team will have regularly scheduled meetings during the period of study implementation, and additional ad hoc calls will be convened if required.

The study site is responsible for continuous close monitoring and management of AEs. The study site investigators are responsible for the initial evaluation and reporting of safety information at the participant level, and for alerting the Protocol Team if unexpected concerns arise. The site will have SOPs describing methods for AE reporting and toxicity management to ensure that AEs are reported and managed in accordance with the protocol and for alerting the Protocol Team if unexpected concerns arise.

7.2 Adverse Event Definition and Reporting

An AE is defined as any untoward medical occurrence in a clinical research participant administered a study product and which does not necessarily have a causal relationship with it. As such, an AE can be an unfavorable or unintended sign (including an abnormal laboratory finding, for example), symptom or disease temporally associated with the use of a study product, whether or not considered related to the product.

As daily oral FTC/TDF for PrEP is a licensed medication, we will focus assessment of AEs on the known toxicity profile of the medication, including creatinine elevations / decreases in creatinine clearance, bone fractures / toxicity, and symptoms associated with a start-up syndrome (e.g. diarrhea, nausea, headache, abdominal gas). A targeted symptom review will be performed at each visit using a symptom checklist focused on symptoms associated with FTC/TDF. The severity of these symptoms will be graded according to the following scale in order to aid clinical management of symptoms.

GRADE 1 MILD	GRADE 2 MODERATE	GRADE 3 SEVERE	GRADE 4 POTENTIALLY LIFE-THREATENING
Mild symptoms causing no or minimal interference with usual social & functional activities with intervention not indicated	Moderate symptoms causing greater than minimal interference with usual social & functional activities with intervention indicated	Severe symptoms causing inability to perform usual social & functional activities with intervention or hospitalization indicated	Potentially life-threatening symptoms causing inability to perform basic self-care functions with intervention indicated to prevent permanent impairment, persistent disability, or death

Abnormal creatinine values will be graded according to the following scale:

PARAMETER	GRADE 1 MILD	GRADE 2 MODERATE	GRADE 3 SEVERE	GRADE 4 POTENTIALLY LIFE- THREATENING
Creatinine, High	1.1 to 1.3 x ULN	> 1.3 to 1.8 x ULN OR Increase of > 0.3 mg/dL above baseline	> 1.8 to < 3.5 x ULN OR Increase of 1.5 to < 2.0 x above baseline	\geq 3.5 x ULN OR Increase of \geq 2.0 x above baseline

22

Study participants will be provided a telephone number and contact information for an oncall clinician and will be instructed to contact the clinician to report any AEs as-needed. For life-threatening events, participants will also be instructed to seek immediate emergency care. At the time a laboratory AE requiring retesting or follow-up is identified, participants will be called back to the clinic if possible, and will be followed as deemed clinically appropriate. All participants reporting any AE assessed as related to FTC/TDF administration (see Section 7.3) will be followed clinically, until the AE resolves (returns to baseline) or stabilizes.

7.3 Assignment of Relationship to FTC/TDF

Relatedness is an assessment made by a study clinician of whether or not the event is related to the TDF/FTC administration. The relationship of all clinically relevant AEs to the FTC/TDF will be assessed per the clinical judgment of the investigator based on the package insert.

7.4 Reporting Requirements for this Study

The site investigator will report an adverse event to the local IRB if study staff determines it may qualify as a Serious or Unexpected Adverse Event that is assessed to be related to study product. An adverse event is defined as being unexpected if the event exceeds the nature, severity or frequency described in the current IRB Application including the protocol, consent form and prescribing information.

A serious adverse event (SAE) includes any AE that meets any of the following criteria:

- o Result in death
- Are life-threatening AEs
- Require inpatient hospitalization or prolongation of existing hospitalization
- Result in persistent or significant disability/incapacity;

An unexpected AE also includes any AE that meets any of the following criteria:

- Results in subject withdrawal from study participation,
- Due to an overdose of study medication, or
- Due to a deviation from the IRB approved study protocol

In addition, all SAEs will be reported to the Protocol Team within 72 hours of recognition by study staff.

7.5 Social Impact Reporting

Although the study site will make every effort to protect participant privacy and confidentiality, it is possible that participants' involvement in the study could become known to others, and that a negative social impact may result (e.g. participants could be perceived as being HIV-infected or at "high risk" for HIV infection). For example, participants could be treated unfairly, or could have problems being accepted by their families and/or communities. Negative social impacts from use of the app will also be monitored, such as unintended loss of privacy or confidentiality. A formal survey about positive and negative social impacts will be administered at week 12 and 24; however, participants will be able to report negative social impacts at all regular visits. In the event that a participant reports a negative social impact, every effort will be made by study staff to provide appropriate care

and counseling to the participant as necessary, and/or referral to appropriate resources for the safety of the participant. Each site will provide such care and counseling in accordance with standardized guidance. While maintaining participant confidentiality, the study site may engage its Community Advisory Board (CAB) in exploring the social context surrounding instances of social impacts, to minimize the potential occurrence of such an impact.

8.0 Laboratory Specimens and Biohazard Containment

8.1 Local Laboratory Specimens

Specimens will be collected for testing at the local laboratory. All testing will be done as part of standard of care except DBS. Local laboratory evaluations/procedures will include:

- HIV testing
- Serum creatinine for creatinine clearance
- HBV testing (HBsAg)
- Syphilis testing
- Urine GC/CT testing
- Oral and rectal GC/CT testing

US local laboratories must be certified under the Clinical Laboratory Improvement Amendments (CLIA-certified). Rapid HIV testing may be performed under a CLIA-waiver at the research clinic site.

The study site will adhere to standards of Good Clinical Laboratory Practice (GCLP), and local standard operating procedures for specimen management including proper collection, processing, labeling, transport, and temporary storage of specimens.

8.2 Dried Blood Spots (DBS)

Dried blood spot (DBS) specimens will be collected at the week 6, 12, 18, and 24 visits. Specimens will be frozen and batch shipped to the University of Colorado Pharmacology Laboratory for testing of TDF-DP and FTC-TP drug concentrations.

8.3 Biohazard Containment

As the transmission of HIV and other blood-borne pathogens can occur through contact with contaminated needles, blood, and blood products, appropriate blood and secretion precautions will be employed by all personnel in the drawing of blood and shipping and handling of all specimens for this study, as currently recommended by the United States Centers for Disease Control and Prevention (CDC). All infectious specimens will be transported in accordance with United States Code of Federal Regulations (42 CFR 72).

9.0 Administrative Procedures

9.1 Training

Recruiters and staff who collect data will complete CITI, GCP, and Human Subjects training, and also a minimum of one hour of training on recruitment procedures, use of the DOT Diary app, and all study instruments. Trained qualitative interviewers will conduct the in-depth interviews and code the responses.

9.2 Confidentiality

All staff are required to sign an oath of confidentiality and receive annual training on maintaining confidentiality, privacy, and handling questions about study participants from friends, employees, and insurance companies. Study staff will discuss any privacy concerns the participant may have regarding the need to contact them, via phone or e-mail, and contact methods will be tailored accordingly. A participant's involvement in this study will not be divulged without the subject's written permission, except as necessary for monitoring by the sponsor and/or its contractors; other government and regulatory authorities, and/or the local IRBs.

Information collected from subjects will be handled in the most confidential manner possible. All data will be coded by a subject number. Personal identifier records will be kept in a password protected computer files and double-locked cabinet at the study site, and any forms with identifying information will be stored separately from other study data. Digital audio and video recordings will be encrypted and stored on password protected computers until destroyed. A Business Associates Agreement for HIPAA has been established with AiCure to ensure confidentiality and security of data stored by AiCure. Identifiable information transmitted to AiCure will not be used for any non-study purposes such as business or marketing. In case of hard drive failure, backup copies of video data will be stored for safekeeping as encrypted volumes. Transcripts of the recordings will be transcribed in such a way as to not have any identifying information present. Participation in study visits will take place in a private office. Questionnaires and surveys will not include any personal identifiers.

Participant phone numbers stored by AiCure will be destroyed at the end of the study and will not be used for any non-study purposes or by AiCure staff.

Each patient will assign and maintain their own password for access to the app and any data therein. Any patient-related data stored in the local device, including sexual history data, will be stored in an encrypted state at all times, and will be unencrypted only when access is requested after password confirmation by the user.

9.3 Informed Consent

The informed consent process will conform to local IRB consent standards. Informed consent will be written and obtained at the study site in a private room, before any study procedures are initiated. Potential participants will be given a copy of the informed consent form and the Experimental Subject's Bill of Rights, and a study staff member will offer to review the form with the participant, and answer any questions the participant may have. The informed consent will be witnessed by a member of the study staff. A copy of the signed form will be given to the participant and the original will be kept in a separate, locked file.

DOT Diary Longitudinal Pilot Statistical Analysis Plan

NCT03771638

PI: [name] Date: April 5, 2019

Statistical Analysis Plan

Primary Objectives

To assess the effect of DOT Diary on PrEP adherence as measured by TFV-DP in DBS among young MSM initiating PrEP. We will use GEE logistic models to estimate the average effect of assignment to DOT Diary on repeated TFV-DP levels ≥700 fmol/punch, which are consistent with taking 4-7 PrEP doses per week. In exploratory analyses, we will examine whether the between-group difference increases over time. We will also use analogous GEE linear models to estimate the effects of D2 on log-transformed TFV-DP levels, as well as GEE proportional odds models for an ordinal outcome defined as TFV-DP levels consistent with <2, 2-3, and 4-7 doses per week, using cut-points determined by pharmacokinetic benchmarks established through directly-observed dosing.²⁸ To help with interpretation of these results, retention in the study will at each 6-week visit will be reported. Minimum detectable effects (MDEs). We used data from the EPIC study to estimate the baseline level and intraclass correlation (ICC) of the repeated binary measures of DBS TFV-DP levels ≥700 fmol/punch as 60% and 0.69 respectively, and retention of 80% of participants at 24 weeks. Under these assumptions, we will have 80% power in 2-sided tests with a type-I error rate of 5% to detect average between-group differences in adherence of 23 percentage points.

To evaluate the concordance of TFV-DP and FTC-TP in DBS with adherence measured by DOT Diary. Validation of DOT will focus on concordance between aDOT-based assessments of PrEP adherence by the AiCure device with four DBS measurements. *First*, we will use a pharmacokinetic (PK) model with parameters estimated in the DOT-DBS Study (NCT02022657) to calculate the expected TFV-DP levels when each DBS is obtained, based on the aDOT-confirmed pattern of pill-taking over the previous 6 weeks, as assessed using aDOT-confirmed results. In sensitivity analyses, we will include self-reported pill-taking. We will then estimate the correlation between these predictions and observed TFV-DP levels based on DBS, and scatterplot the two measures against each other, with a Lowess smooth. As an additional measure of concordance, we will estimate the proportion of 90% prediction intervals obtained from the PK model that include the measured DBS TFV-DP levels. **Second**, we will also use aDOT-confirmed aDOT records of pill-taking over the previous 4 and 8 weeks to estimate the average number of PrEP doses per week taken by each participant, then estimate concordance of aDOT- and DBS-based indicators for protective dosing of 4-7 doses/week, with 95% confidence intervals. The DBS indicator will be defined by TFV-DP levels ≥700 fmol/punch. We will also assess concordance of aDOT- and DBSbased measures of <2, 2-3, and 4-7 doses per week, using the Kappa statistic. Third, we will estimate concordance between an aDOT-based indicator for any PrEP use over the previous 48 hours with an indicator for detection of FTC-TP in DBS, again with 95% confidence intervals. Margins of sampling error (MSEs). The expected sample of 240 DBS (an average of 3.59 from each of 67 participants, accounting for cumulative 20% loss to follow-up over 24 weeks) will allow us to estimate the concordance of paired binary measures within MSEs of 6.3-8.4 percentage points, depending on the sample concordance. MSEs for concordance of DOT results with detection of FTC-TP will be similar.

To assess the acceptability and ease of use of DOT Diary over a 24 week period.

Acceptability and ease of use will be measured using the System Usability Scale (SUS) and

Client Satisfaction Questionnaire (CSQ-8) adapted for use in the DOT Diary Longitudinal pilot.²⁹ Average values of our measures of acceptability and ease of use will be estimated with 95% confidence intervals. *MSEs.* The estimated sample of 54 participants providing end of study data will allow us to estimate mean SUS and CSQ-8 scores within MSEs of 0.27 standard deviations (SDs).

Secondary Objectives

To assess PrEP coverage of sexual acts (prevention-effectiveness adherence) as measured by DOT Diary. We will estimate the probability of coverage of condomless receptive sexual acts in each period, with sexual acts treated as trials, and coverage as success. Confidence intervals will be obtained using GEE binomial models, with robust standard errors will be used to account for within-subject correlation as well as over-dispersion of the binomial outcome. *MSEs.* We also used EPIC data to estimate the average number of condomless receptive sexual acts per participant as ~7. Under this assumption, we will be able to estimate coverage probabilities within MSEs of 4-10 percentage points, depending on coverage levels and the ICC of coverage across episodes.

To evaluate the daily use of the DOT and diary components of DOT Diary through 24 weeks of follow-up. We will estimate the average use of DOT and the diary, as proportions of days and weeks on study, respectively. In the primary ITT analysis, participants will be included in the denominator through 24 weeks, regardless of dropout. In a per-protocol analysis, participants will be omitted from the denominator after dropout. *MSEs.* Proportions will be estimated within MSEs of 7-12 percentage points, depending on the sample proportions.

Subgroup analyses. Four pre-specified subgroup analyses will conducted in which interaction terms will be added to the primary GEE logistic models for protective DBS levels, to assess modification of treatment effects by 1. site; 2. age (categorized as <25 and 25+); 3. race/ethnicity, categorized as African American or Latinx vs White or other; and 4. prior PrEP use. Within-subgroup effect estimates will be presented only if the corresponding omnibus test for treatment-subgroup interaction is statistically significant at P<0.15, and results will be presented as exploratory.

Exploratory analyses of treatment effect mechanism. Standard per-protocol analyses focused on treatment effects among participants who are adherent to blinded placebo-controlled treatment are not feasible in a context where use of the app is directly tied to pill counts and DBS results. For the same reason, the design also precludes standard mediation analysis assessing treatment effects on the mediator as well as effects on the primary outcome before and after adjustment for the mediator. To better understand how any effect occurs, we will explore associations between aDOT-confirmed pill counts and time spent using the app overall, as well as time spent with the sexual diary, within the intervention arm. In addition, we will assess the relationships among sexual risk, as measured via the diary, pill counts, and DBS results.

Qualitative Data analysis. Recordings of the in-depth interviews (IDIs) will be analyzed using DeDoose software for qualitative analysis. The analysis team will include members at both San Francisco and Atlanta study site, as well as a representative from AiCure. Interviewers will complete a debrief report promptly following each interview to capture results relevant to the study objectives. Debrief reports will also include an assessment of

whether the interview merits additional in-depth analysis. Debriefing reports have been shown to be of sufficiently high quality to use as a primary source.³⁰ Debrief reports and selected transcripts will be reviewed for emergent themes and results relevant to the study objectives. Team members will create summary reports based on this analysis for use in providing feedback and suggestions in achieving study goals, and to contribute to manuscript development. Debrief reports will be reviewed promptly in order to provide feedback and suggestions for subsequent interviews. The first two audio recorded interviews and resulting debrief report at each site will be reviewed by a member of the team at the other site in order to assure uniformity in interview approaches and information included in debrief reports.

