In 2014, men who have sex with men (MSM) accounted for 70% of new HIV diagnoses in the United States, and MSM are the only US population in which new HIV infections are rising.¹⁰ Black and Latino men are at particularly high risk, with HIV infection rates estimated to be 6.6 and 2.9 fold higher than among White men. Disparities in HIV prevalence increased in 2008-2011, and grew fastest in the youngest age groups.¹¹ Young MSM (YMSM) accounted for nearly 20% of the estimated HIV diagnoses nationwide and over 80% of new HIV infections among youth in 2014. Furthermore, Black and Latino YMSM accounting for 55% and 33% of HIV infections among YMSM, respectively.¹⁰ Despite the promise of PrEP in preventing HIV acquisition among YMSM, PrEP uptake has been low in this vulnerable population. According to national prescription data, youth under 24 are the least likely to initiate PrEP, with only 9% of PrEP initiations in 2015 occurring in this age group.¹² In a recent national survey, only half of YMSM aged 15-24 had heard of PrEP, and 1.7% had ever used PrEP.¹³ Demonstration projects also highlight challenges with PrEP uptake and adherence. In the US Demo Project of 550 MSM, only 20% were age 25 or under, and PrEP uptake was lower among younger, non-white. and less educated persons.¹⁴ In multivariate analysis, the only independent predictors of adherence as measured by tenofovir diphosphate levels in dried blood spots were Black race (adjusted odds ratio, aOR 0.28, 95% CI 0.12-0.64) and enrollment in Miami (aOR 0.32, 95% CI 0.17-0.60).¹⁵ Self-reported adherence, pill counts, and medication possession ratios did not completely explain the disparities in TFV-DP levels. Similar findings were seen in the ATN 110 study of YMSM aged 18-22, where PrEP uptake was only 16%, and PrEP adherence was lower among Black YMSM and declined overall during follow-up, particularly with less frequent visits.¹⁶ Clearly, future PrEP studies must include sizeable numbers of African American, Latino, and young MSM, who are at high risk for HIV and may require timely adherence support, triggered by an accurate measure of adherence. Additionally, studies of on-demand (or 2-1-1) PrEP, in which 2 doses of TDF/FTC PrEP are taken in the 24 hours prior to sex, and 1 dose each taken 24 and 48 hours later, have demonstrated promise in a randomized study[refs] and

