5.0 Study Design

5.1 Overview

This is a pilot study to assess the effect of DOT diary on PrEP adherence among YMSM, and to assess the acceptability and ease of use of the DOT Diary app in this population over a 24 week period. We will enroll up to 100 total participants (approximately 50 per city) who have not been on PrEP in the last 4 months (PrEP naïve participants are preferred) and are willing to initiate PrEP at the enrollment visit. Participants will be randomized 2:1 to receive (intervention arm) or not receive (control arm) the DOT Diary app at enrollment. Participants will return for follow-up visits at 6, 12, 18, and 24 weeks for safety assessments, pharmacologic measures of adherence (tenofovir diphosphate [TFV-DP] and emtricitabine triphosphate [FTC-TP]), study drug provision, and quantitative and qualitative acceptability assessments.

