5.3 Randomization

Participants will be randomized in a 2:1 ratio to the intervention (N=67) or control (N=33) conditions, using randomly-permuted blocks of randomly selected size 3 and 6, stratified by site (San Francisco, Atlanta). The randomization scheme will be generated and archived by the study statistician, and implemented in RedCap.

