- b. We will use aDOT records of pill-taking over the previous 4 and 8 weeks to estimate the average number of PrEP doses per week taken by each participant, then estimate concordance of aDOT- and DBS-based indicators for protective dosing of 4-7 doses/week, with 95% confidence intervals. The DBS indicator will be defined by TFV-DP levels ≥700 fmol/punch. We will also assess concordance of aDOT- and DBS-based measures of <2, 2-3, and 4-7 doses per week, using the Kappa statistic.
- c. We will estimate concordance between an aDOT-based indicator for any PrEP use over the previous 48 hours with an indicator for detection of FTC-TP in DBS, again with 95% confidence intervals.

Margins of sampling error (MSEs). The expected sample of 240 DBS (an average of 3.59 from each of 67 participants, accounting for cumulative 20% loss to follow-up over 24 weeks) will allow us to estimate the concordance of paired binary measures within MSEs of 6.3-8.4 percentage points, depending on the sample concordance. MSEs for concordance of DOT results with detection of FTC-TP will be similar.

3. To assess the acceptability and ease of use of DOT Diary over a 24 week period

Acceptability and ease of use will be measured using the System Usability Scale (SUS) and Client Satisfaction Questionnaire (CSQ-8) adapted for use in the DOT Diary Longitudinal pilot.³⁰ Average values of our measures of acceptability and ease of use will be estimated with 95% confidence intervals.

MSEs. The estimated sample of 54 participants providing end of study data will allow us to estimate mean SUS and CSQ-8 scores within MSEs of 0.27 standard deviations (SDs).

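### Randomization is stratified by site, but the primary GEE logistic model names only assignment; site should be stated as a main effect, since omitting it makes the test conservative if adherence differs between sites.

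*SAP*

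**What the plan says.** Protocol 5.3 allocates 2:1 (67 intervention, 33 control) "using randomly-permuted blocks of randomly selected size 3 and 6, stratified by site (San Francisco, Atlanta"). Protocol 5.1 sets the size: "We will enroll up to 100 total participants (approximately 50 per city").

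The primary analysis, in SAP Primary Objectives and in the same words in Protocol 6.2.1, is: "We will use GEE logistic models to estimate the average effect of assignment to DOT Diary on repeated TFV-DP levels" at or above 700 fmol/punch. Assignment is the only model term named. Site appears once, under Subgroup analyses in the SAP, where "interaction terms will be added to the primary GEE logistic models for protective DBS levels, to assess modification of treatment effects by 1. site" and by three other factors. Those results are to be presented as exploratory. Adding an interaction to the primary model does not say whether a site main effect is already there.

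Both documents state 80% power, two-sided at 5%, for "average between-group differences in adherence of 23 percentage points", from a 60% baseline level, an ICC of 0.69 and 80% retention at 24 weeks. The power statement does not mention site.

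**The concern.** Permuted blocks within site hold the arms close to 2:1 in each city, so differences between cities contribute almost nothing to the chance variation of the treatment contrast. A model without site does not know this. It leaves the between-site variation in the residual and counts it in the standard error. If the cities differ in adherence, the standard error is too large for the design and the true test size falls below the stated 5%.

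The error is in the safe direction. What is at stake is a test that does not have its stated size, in a trial with 33 controls, and an analysis choice left open. Including or omitting site gives different p-values and different odds ratios, and the SAP does not say which is primary.

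**Working it through.** **1. The plan's own figure.** Inputs are 67 and 33 participants, 60% against 83%, ICC 0.69, and Protocol 6.2.1's "an average of 3.59 from each of 67 participants".

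- Design effect = 1 + (3.59 − 1) × 0.69 = 2.787.
- Effective sizes: 33 × 3.59 / 2.787 = 42.5 and 67 × 3.59 / 2.787 = 86.3.
- Pooled proportion = (33 × 0.60 + 67 × 0.83) / 100 = 0.754. Standard error under the null = √[0.754 × 0.246 × (1/42.5 + 1/86.3)] = 0.0807. Under the alternative = √[0.24/42.5 + 0.1411/86.3] = 0.0853.
- Power = Φ[(0.23 − 1.96 × 0.0807) / 0.0853] = Φ(0.842) = 80.0%.

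The 23-point figure reproduces without a site term.

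**2. Range of site gaps (assumed).** The documents give no San Francisco-Atlanta adherence gap. Their only between-city figure for TFV-DP in DBS is in Protocol 1.0: "enrollment in Miami (aOR 0.32, 95% CI 0.17-0.60"). It is an adjusted ratio for a city outside this trial and is used here only to choose a range. For two equal sites averaging 60%, an odds ratio of 0.32 (0.60, 0.17) equals a gap of 26.5 (12.2, 39.6) points. Gaps from 0 to 41 points are shown.

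**3. Analytic size without site.** Variance of a participant's mean = 0.24 × 2.787 / 3.59 = 0.1863. With two equal sites, the share due to site is s = (gap/2)² / 0.1863. The estimated variance includes this share and the true variance does not, so size = 2 × [1 − Φ(1.96 / √(1 − s))]. At 27 points, s = 0.0182 / 0.1863 = 0.098 and size = 3.9%.

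**4. Simulation.** Each cell has 40,000 trials: 50 per site, blocks of 3 and 6 within site, 60% mean control adherence, and assumed attendance of 100, 92.8, 86.2 and 80% (sum 3.59). Total ICC is held at 0.69. The model is a GEE logistic with exchangeable working correlation fixed at 0.69 and a two-sided 5% Wald test with robust variance. KC is the Kauermann-Carroll correction. Monte Carlo error is about 0.11 points for size and 0.20 for power.

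Type I error, %:

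| Assumed gap, points | s | Analytic, no site | Simulated, no site | Simulated, site | Site + KC |
|---|---|---|---|---|---|
| 0 | 0 | 5.0 | 5.0 | 5.1 | 4.75 |
| 13 | 0.023 | 4.7 | 4.6 | 5.0 | 4.65 |
| 20 | 0.054 | 4.4 | 4.4 | 5.2 | 4.72 |
| 27 | 0.098 | 3.9 | 4.0 | 5.2 | 4.83 |
| 35 | 0.164 | 3.2 | 3.3 | 5.2 | 4.80 |
| 41 | 0.226 | 2.6 | 2.7 | 5.4 | 4.94 |

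Without site, the mean robust standard error of the log odds ratio is 0.98, 1.00, 1.01, 1.04, 1.07 and 1.12 times its true standard deviation across these gaps. With site it is 0.97 to 0.98 times.

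**5. Power and precision.** The effect is a common within-site odds ratio giving +23 points overall. Calibrated power sets each test to 5% using its own simulated null distribution.

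| Assumed gap, points | Nominal, no site | Nominal, site | Nominal, site + KC | Calibrated, no site | Calibrated, site |
|---|---|---|---|---|---|
| 0 | 79.9 | 80.1 | 79.2 | 79.8 | 79.8 |
| 13 | 80.1 | 80.9 | 79.9 | 81.0 | 80.9 |
| 20 | 80.3 | 81.5 | 80.6 | 81.6 | 81.2 |
| 27 | 81.2 | 83.3 | 82.4 | 83.5 | 82.8 |
| 35 | 82.0 | 85.3 | 84.5 | 86.1 | 84.9 |
| 41 | 82.2 | 86.5 | 85.8 | 87.7 | 85.9 |

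The nominal gain with site (81.2 to 83.3% at 27 points) is recovered test size, not new information: at equal size the adjusted test is no more powerful. Precision agrees. The null standard deviation of the risk difference, without and with site, is 0.0923 and 0.0924 at no gap, and 0.0878 and 0.0877 at 27 points.

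**6. Different modelling choices.** A simulation with independence working correlation and ICC 0.69 held within site gave sizes without site of 4.8, 5.0, 4.6, 4.1 and 3.1% at gaps of 0, 10, 20, 30 and 40 points. With site they were 5.0, 5.2, 5.2, 5.6 and 5.4%. Direction and size of the conservatism agree. Its nominal power gain was larger (76.0 to 81.6% at 30 points), but it added 23 points in each site, which takes the higher site to 0.75 + 0.23 = 98%.

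**The case against.** The harm is slight and conditional. With no site gap there is no effect, and at 10 points or less it is negligible. The range is borrowed from a city outside the trial, and the largest departures need gaps of 35 to 41 points. All of this stands.

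The fix is not free of side effects. Site alone moves the test slightly above 5%. With the correction, nominal power is 79.2 against 79.9% for the plan as written at no gap, and about level up to 20 points. The odds ratio also becomes site-conditional: 60% to 83% is 3.25 marginally but 3.51 within site at a 27-point gap, while the plan states its target difference in percentage points. These points stand as costs. Both odds ratios equal 1 under no effect, so the null hypothesis is unchanged.

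Finally, silence is not exclusion. The SAP also names no visit term, working correlation or variance estimator, and site may be intended. That is fair, and it is a reason to write the term down. Protocol 1.0 itself describes the two regions as differing in sociodemographics and in PrEP availability and uptake, so a difference in adherence is plausible. None of these points makes the site-omitted standard error right for a site-stratified design.

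**Conclusion.** The point holds and is small. The primary model as written does not include the factor the trial is randomized on. If the sites differ, the test is conservative: about 4.4% at a 20-point gap and 4.0% at 27, against a stated 5%. The size rests on an assumed gap, total ICC 0.69, 50 participants per site and the assumed attendance pattern; the direction follows from the stratified design. The test does not produce extra false positives, the estimator is not materially less precise without site, and the power statement needs no correction. The stronger reason to act is that the choice is made before data are seen. It should be made, as a low-cost clarification.

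**What to change.** State in the SAP that site is a main-effect term in the primary GEE logistic model, that the primary test is on the assignment coefficient of that model, and that the result is a site-adjusted odds ratio. If the test is to stay at or below 5%, name a Kauermann-Carroll corrected robust standard error.

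Optionally, report a site-standardized risk difference beside the odds ratio, so the result can be read against the 23-point figure. Give it a Mancl-DeRouen corrected interval, which covers 94.7 to 95.1% against 93.8 to 94.3% uncorrected. Because that interval and the primary test use different corrections and scales, say that the conclusion rests on the test.

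The cost is one sentence, one model term and one degree of freedom, with no new data. The correction takes 0.7 to 1.0 points of nominal power, and at equal test size the adjusted test has 0.7 to 1.8 points less power at gaps of 27 to 41. The odds ratio must be read as within-site.
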